4.2 Patient Characteristics

Baseline characteristics for continuous variables will be summarized by mean, standard deviation, minimum, median, and maximum values; and baseline characteristics for discrete variables will be summarized with frequency and percentages.

4.2.1 Demographics and Baseline Characteristics

Demographic data such as age, sex, ethnicity, and race will be summarized. Baseline characteristics at the initial study will also be tabulated.

4.3 Efficacy Analyses

All efficacy endpoints will be analyzed based on the ITT population. The analyses will be repeated for PP population for outcomes defined for BAD total score and PGI-I as sensitivity analyses. Detailed definition of BAD scale and PGI-I can be found in section 7.1 of the study protocol.

4.3.1 Efficacy Endpoints

All patients:

For the efficacy measures of BAD (total score and by body region) and PGI-I, the value at each of the measurement time points defined in section 4 will be determined and summarized using descriptive statistics for all patients on DFP treatment. Similar data will also be presented by the treatment group received in initial study.

A paired t-test will be used to assess the statistical significance of the changes in these efficacy outcomes from baseline to the end of study (Visit 4, month 18 or 36 as defined in section 4).

For the BAD total score and for PGI-I, the proportions of patients determined to be responders at the end of study (Visit 4) will be calculated and presented along with 95% confidence intervals.

The mean trajectory of BAD (total score and by body region) and PGI-I by time will be plotted. The longitudinal trend for BAD total score and by body region will be explored by the MMRM model with time modelled as a continuous variable as defined in section 4 for all time points where patients were on DFP.

Patients who received placebo in initial study:

For the efficacy measures of BAD (total score and by body region) and PGI-I, the value at each of the measurement time points defined in section 4 will be determined and summarized using descriptive statistics for each study period.

A paired t-test will be used to compare the change in BAD (total score and by body region) between the start and completion of the initial study to that between the start and completion of the extension study. The same test will be repeated for the PGI-I data.

The incidence of changes in DBS settings and outcome impacting medication use as well as the frequency of PRN drug or rescue medication use will be tabulated and compared between the initial study and the extension study. If statistically significant imbalances are detected, they will be adjusted accordingly for the comparison of changes in BAD and PGI-I between the initial study and the extension study by using the MMRM model as defined in section 4.

For the BAD total score and for PGI-I, McNemar's test will be used to compare the proportion of responders in the initial study with the proportion of responders in the extension study.

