Schedule of treatment and specimen collection:	
All patients will be scheduled to take deferiprone daily, 2 times a day, for up to 18 months.
 
Safety and efficacy assessments will be conducted at the following time points:
 
 • Hematology: Weekly up to Visit 4 (End of Study) or early termination • Blood chemistry: Visits 1, 2, 3, and 4 or early termination • ECG: Visits 1 and 4 or early termination • BAD: Visits 1, 2, 3, and 4 or early termination • PGI-I: Visits 2, 3, and 4 or early termination * 
* The PGI-I will be conducted at Visit 1 as well, but its data on that day will be applicable only to the initial study (for which this is the last visit), not to the extension study.
	
Statistical methods:	
Safety Analysis
 
The incidences of AEs and SAEs reported during deferiprone therapy for all patients, from the start of TIRCON2012V1 to the completion of TIRCON2012V1-EXT, will be tabulated. Similar tables will be produced for the severity of AEs and for their relationship to the study medication. Time to onset and duration of all AEs with an incidence of >5%, and of any AEs of special interest (e.g., worsening of dystonia), will be summarized with descriptive statistics.
 
The percentage of discontinuations due to AEs will be calculated, and the AEs leading to discontinuation will be summarized in a frequency table by preferred term.
 
Laboratory data (hematology and blood chemistry) will be summarized using descriptive statistics for continuous variables and frequency tables for discrete variables. The incidences of out-of-range data will be tabulated, and the changes from baseline to the end of study will be examined using shift tables.
 
Efficacy Analysis
 
For the efficacy measures of BAD (total score and by body region) and PGI-I, the change from baseline to each of the measurement time points will be determined and summarized using descriptive statistics. A paired t-test will be used to assess the statistical significance of the changes in these efficacy outcomes from baseline to Visit 4. For the BAD total score and for PGI-I, the proportions of patients determined to be responders at Visit 4 will be calculated and presented along with 95% confidence intervals.
	

Name of Sponsor: ApoPharma Inc.	Individual Study Table Referring to Part of the Dossier Volume: Page:	(For National Authority Use Only)
Name of Finished Product: Deferiprone		

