7.1.2 Patient Global Impression of Improvement

The Patient Global Impression of Improvement (PGI-I) is a global index used to rate the response of a condition to a therapy. Patients are asked at each post-Week 0 visit to rate their overall condition since Visit 1 of the extension study on a 7-point rating scale: 1 = very much improved, 2 = much improved, 3 = minimally improved, 4 = no change, 5 = minimally worse, 6 = much worse, and 7 = very much worse. In cases where the patient cannot complete the scale by him/herself, the parent or legal representative will complete the scale. See [Appendix 5](#).

The PGI-I will be administered at Visits 2, 3, and 4 (or early termination).

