9.1.2 Secondary Endpoints

All patients:

- Change in the BAD total score from baseline (defined as prior to the start of deferiprone therapy) to Visit 4, as assessed by central evaluation of videotapes
- Proportion of patients with improved or unchanged BAD scale total score between baseline and Visit 4 (responder analysis)
- Change from baseline to Visit 4 in BAD scale score per body region (eyes, mouth, neck, trunk, and each upper and lower extremity), as assessed by central evaluation of videotapes
- Change in score on the PGI-I from baseline to Visit 4
- Proportion of patients showing an improvement on PGI-I at Visit 4 (responder analysis)

The time points for these efficacy endpoints are defined as follows:

- For patients who received deferiprone in the earlier study, the baseline visit of that study will be treated as the baseline visit of TIRCON2012V1-EXT as well. Thus, Visit 1 of the extension study (Week 0) will be Year 1.5, and Visit 4 (Week 78) will be Year 3.
- For patients who received placebo in the earlier study, Visit 1 of the extension study (Week 0) will be the baseline visit. Thus, Visit 4 (Week 78) will be Year 1.5.

Patients who received placebo in initial study:

For this group only, for each measure, the changes seen between the start and completion of study TIRCON2012V1 (i.e., following 18 months on placebo) will be compared against the changes seen between the start and completion of study TIRCON2012V1-EXT (i.e., following 18 months on deferiprone), as follows:

- Comparison of change in BAD total score from baseline to completion of the initial study vs. change in BAD total score from baseline to completion of the extension study
- Comparison of the proportion of patients with improved or unchanged BAD scale total score between baseline and completion of the initial study vs. the proportion with improved or unchanged BAD scale total score from baseline to completion of the extension study (responder analysis)
- Comparison of the change in BAD score per body region between baseline and completion of the initial study vs. change in BAD score per body region between baseline and completion of the extension study
- Comparison of change in PGI-I score from baseline to completion of the initial study vs. change in PGI-I score from baseline to completion of the extension study

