3.6 Statistical Software and Level of Significance

All statistical analyses will be performed using SAS (version 9.3 or higher) on Windows operating system. Null hypotheses tested are that there are no differences in true parameter between comparison groups, unless otherwise stated. A two-sided *p*-value of 0.05 will be used as the significance level for the determination of statistical significance in all statistical tests.

4 Statistical Analyses

The efficacy endpoints are defined as follows:

All patients:

- Change in the BAD total score from baseline (defined as prior to the start of deferiprone therapy) to Visit 4, as assessed by central evaluation of videotapes
- Proportion of patients with improved or unchanged BAD scale total score between baseline and Visit 4 (responder analysis, responders defined as change in BAD total score to be ≤ 0)
- Change from baseline to Visit 4 in BAD scale score per body region (eyes, mouth, neck, trunk, and each upper and lower extremity), as assessed by central evaluation of videotapes
- PGI-I score at Visit 4
- Proportion of patients showing an improvement on PGI-I at Visit 4 (responder analysis, responders are defined as patients whose conditions have not deteriorated; patients who have “no change”, or are “minimally improved”, “much improved” or “very much improved” in the PGI-I questionnaire at the last study visit)

The time points for these efficacy endpoints are defined as follows:

- For patients who received deferiprone in the initial study, the baseline visit of that study will be treated as the baseline visit of TIRCON2012V1-EXT as well. Thus, Visit 1 of the extension study (Week 0) will be Year 1.5 (month 18), and Visit 4 (Week 78) will be Year 3 (month 36).
- For patients who received placebo in the initial study, Visit 1 of the extension study (Week 0) will be the baseline visit. Thus, Visit 4 (Week 78) will be Year 1.5 (month 18).

Patients who received placebo in initial study:

For this group only, for each measure, the changes seen between the start and completion of the initial study (TIRCON2012V1) (i.e., following 18 months on placebo) will be compared against the changes seen between the start and completion of extension study (TIRCON2012V1-EXT) (i.e., following 18 months on deferiprone), as follows:

- Comparison of change in BAD total score from baseline to completion of the initial study vs. change in BAD total score from baseline to completion of the extension study

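### The pooled Visit 4 PGI-I is tested and headed as change from baseline, but for the 44 patients already on deferiprone it rates change only since Month 18; its one-group paired t-test has no stated null, and its responder endpoint is named improvement but counts no change

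*SAP*

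**What the plan says.** **Reference point of the rating.** Protocol 7.1.2 asks patients at each visit after Week 0 to "rate their overall condition since Visit 1 of the extension study on a 7-point rating scale". SAP 4.3 adopts this definition: "Detailed definition of BAD scale and PGI-I can be found in section 7.1 of the study protocol". The protocol synopsis states the endpoint as running from Visit 1 to Visit 4. It adds that the PGI-I is also given at Visit 1, but "its data on that day will be applicable only to the initial study".

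**Baseline.** SAP section 4 (and Protocol 9.1.2) sets baseline before the start of deferiprone. For patients on deferiprone in the initial study (DFP-DFP), "the baseline visit of that study will be treated as the baseline visit of TIRCON2012V1-EXT as well", so Visit 4 is Month 36. For former placebo patients (Placebo-DFP), Visit 1 is the baseline and Visit 4 is Month 18.

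**Endpoint and test.** Protocol 9.1.2 lists "Change in score on the PGI-I from baseline to Visit 4". The SAP section 4 endpoint list says only PGI-I score at Visit 4. SAP 4.3.1 then uses a paired t-test to "assess the statistical significance of the changes in these efficacy outcomes from baseline to the end of study (Visit 4, month 18 or 36"), and the outcomes meant are BAD and PGI-I. Table 14.2.1.15 has no baseline row for PGI-I. It enters the pooled Visit 4 rating in the *Change from Baseline* column with a paired t-test p-value.

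**Responder.** The endpoint reads "Proportion of patients showing an improvement on PGI-I at Visit 4 (responder analysis". In SAP section 4 the attached rule is that "responders are defined as patients whose conditions have not deteriorated", with no change listed among the qualifying answers.

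**The concern.** PGI-I is the only measure serving the secondary objective of global improvement over time. Three things make its all-patient Visit 4 result hard to read.

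- **Reference point.** Take two DFP-DFP patients, one who worsened over the first 18 months on drug and then held steady, and one who improved and then held. Both rate 4 at Visit 4, both count as responders, and both appear at Month 36. A reader who trusts the column heading would take this as a 36-month result.
- **Null value.** A paired t-test on BAD change has an obvious null of 0. PGI-I runs from 1 to 7, no change is 4, and the SAP does not say what the rating is tested against.
- **Name.** A rate described as improvement that includes unchanged patients can be quoted as something it is not.

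**Working it through.** The plan gives no sample size, power or effect figure for PGI-I, so there is nothing of its own to reproduce beyond the enrolment split in SAP 3.2: 44 + 24 = 68.

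**1. What a Visit 4 rating covers**

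| Group | Enrolled | SAP baseline | SAP time of Visit 4 | Period the patient rates (Protocol 7.1.2) |
|---|---|---|---|---|
| Placebo-DFP | 24 (35.3%) | Visit 1 | Month 18 | Month 0 to 18 on deferiprone |
| DFP-DFP | 44 (64.7%) | Start of initial study | Month 36 | Month 18 to 36 on deferiprone |

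The baseline label is right for 24/68 = 35.3% and wrong for 44/68 = 64.7%. For DFP-DFP the rating covers at most 18 of the 36 labelled months, or nominally 6 or 12 if Visit 2 or Visit 3 is carried forward under SAP 3.5.

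In Table 14.2.1.12 (PGI-I by visit, all patients on deferiprone), Placebo-DFP ratings end at nominal Month 18. The Month 24, 30 and 36 rows, 3 of 6, therefore hold only DFP-DFP ratings made since Month 18. No note says that the reference has reset.

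**2. Size of the labelling effect (illustration, assumed means)**

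Suppose everyone is stable after Visit 1, so the pooled mean is 4.0. If DFP-DFP patients would have rated 4.5 or 5.0 against their pre-deferiprone state, the pooled mean on the labelled scale would be:
- (44 × 4.5 + 24 × 4.0)/68 = 4.32
- (44 × 5.0 + 24 × 4.0)/68 = 4.65

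The documents do not say which, if either, applies.

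**3. The missing null value**

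One-sample t = (mean − reference)/(SD/√n), with n = 68, two-sided, and assumed SD 0.8 to 2.0:

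| Assumed mean | Against 4 | Against 0 |
|---|---|---|
| 4.0 | t = 0, p = 1.0 | t = 41.2 to 16.5 |
| 5.0 | t = 10.3 to 4.1 | t = 51.5 to 20.6 |

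Samples of 68 split between the extreme scores 1 and 7 were also searched. The smallest t against 0 was 7.2 (p = 6 × 10⁻¹⁰). The reference value therefore decides the result. SAP 3.6 gives a null only for differences between comparison groups. The same unreferenced paired t-test is cited for the one-group p-values in Tables 14.2.1.11 and 14.2.1.12, and for the within-period p-values in Table 14.2.2.6.

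**4. The responder name**

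Rate under the SAP rule (score ≤ 4) − improved rate (score ≤ 3) = share scoring 4. Each patient scoring 4 adds 1/68 = 1.5 percentage points to the pooled rate, 1/44 = 2.3 in DFP-DFP and 1/24 = 4.2 in Placebo-DFP. If 20% to 40% score 4 (assumed), the gap is 14/68 = 20.6 to 27/68 = 39.7 points.

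**The case against.** Much can be said for the plan.

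- **The pooled score is coherent.** At Visit 4 both groups rate the same nominal 18 months since Visit 1, and the synopsis states the endpoint in just those terms. This stands. A reader might infer that the pooled PGI-I is invalid or biased; the documents do not support that. The fault is that Protocol 9.1.2, SAP 4.3.1 and Table 14.2.1.15 call it change from baseline, and that those 18 months are the first on drug for one group and the second for the other.
- **By-group results are already planned.** Table 14.2.1.11 gives PGI-I with p-values by initial-study group at each visit, and Table 14.2.1.13 gives responders likewise. This stands, so it would be wrong to say that the plan hides the group difference. Still absent are by-group responder confidence intervals, by-group last-observation or imputed Visit 4 rows, and the note on the reset.
- **A paired t-test is a one-sample test on changes, and 4 is the natural null.** This is fair. A reader might infer that the plan tests the rating against 0, but nothing in the SAP says so. The point is that the null is unstated.
- **The responder rule is open.** The SAP spells it out, it parallels the BAD rule, and the table shells say only Responder in PGI-I. This also stands: nothing is concealed, and the mismatch lies in the endpoint wording.
- **PGI-I is secondary** in an open-label, single-arm study with a safety objective and no power calculation. That limits the weight of the point but does not remove it.

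**Conclusion.** The concern holds as a fault of labelling and specification, and it should be fixed. For 44 of 68 enrolled patients (64.7%; the share in the ITT population may differ), the Visit 4 PGI-I is not a change from the baseline that the SAP sets. The all-patient result can be read as change since extension Visit 1, but not as change since deferiprone began. The one-group p-values have no stated null, and the endpoint's name does not fit its rule.

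This rests on Protocol 7.1.2 governing the rating. Appendix 5 refers only to the beginning of the study without saying which, but 7.1.2 is explicit and lies in the section that the SAP cites.

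The illustrative means and the 20% to 40% share are assumptions; no bias of a given size has been shown. Not affected are the safety endpoints, BAD, the between-period paired t-test and McNemar's test in former placebo patients, and the SAP section 4 statement that PGI-I already measures change, as it applies to the mixed model in those patients, whose baseline is Visit 1.

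**What to change.** - **Reference point.** In all versions of Table 14.2.1.15, head the pooled PGI-I as since extension Visit 1 rather than change from baseline. Footnote the Month 18 reset wherever DFP-DFP ratings span it, including plots. Align Protocol 9.1.2, Protocol Appendix 5 and SAP 4.3.1 with Protocol 7.1.2.
- **By-group rows.** Add PGI-I rows by initial-study group to the main, per-protocol and imputed versions of Tables 14.2.1.15 and 14.2.1.16. Do not split the eight subgroup tables by arm: the two levels of each factor share at most 24 Placebo-DFP patients.
- **Test.** Replace the one-group paired t-tests on PGI-I with a one-sample test against 4, or drop those p-values. Keep the between-period paired test and McNemar's test.
- **Responder.** Report improved (score ≤ 3) and not worsened (score ≤ 4) under those names.

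The cost is text and table-shell changes, with no new data. By-group intervals are wider: at a 50% rate the exact (Clopper-Pearson) 95% interval is 37.6% to 62.4% at n = 68 (half-width 12.4 points), 34.6% to 65.4% at n = 44 (15.4) and 29.1% to 70.9% at n = 24 (20.9). The proportion called improved will be equal or lower.

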3.2 Determination of Sample Size and Study Power

There was no formal sample size and power calculation for this study. All patients who completed TIRCON2012V1 study were invited to enroll in the extension study. Among the 89 subjects randomized in TIRCON2012V1 study, 76 completed the study and 68 subjects were subsequently enrolled in this extension study (44 originally randomized to the deferiprone group and 24 in the placebo group).

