3.5 Missing Data Handling and Derivation Rules

For safety data analysis, no imputation will be performed on the missing data and analysis will be based on observed cases.

For efficacy endpoints, the continuous variables will be summarized and analyzed as recorded on the case report forms (CRFs). If statistically significant imbalances are detected in the incidence of changes in DBS settings and outcome impacting medication use as well as the frequency of PRN drug or rescue medication between the initial study and the extension study, a Mixed-Effect Model Repeated Measure (MMRM) model will be used as the analysis method to compare the change in score from baseline between the initial study and the extension study for patients who received placebo in initial study (TIRCON2012V1) and the analysis will be based on observed cases. If no significant imbalance was detected, the paired t-test will be used as the analysis method and the last observed data will be used.

For the efficacy analysis on all patients who received DFP during the initial and the extension study, the last observation will be used to calculate the change from baseline for patients terminated early. As a sensitivity analysis, for early termination due to worsening of disease conditions or inadequate efficacy of the drug, as indicated in the CRF, the “worst score” method will be used for data imputation. That is, for continuous variables such as BAD total score at a particular time point, the worst score of all patients will be used to impute the missing data at that time point. For categorical variable such as responder, the worst category (treatment failure) will be assigned. For missing data due to missed visit, the last observation will be used to fill the void.

For BAD total score, if one or several component scores cannot be measured, then the same component score from the last visit will be carried forward and if it is also missing, the score from the next visit will be carried backward to fill the missing component score(s) before the total score is calculated.

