Table 14.2.1.13a	Proportions of responders in PGI-I at each follow-up visit by treatment group in initial study – PP population
Table 14.2.1.14	Proportions of responders in PGI-I at each follow-up visit for all patients on DFP – ITT population
Table 14.2.1.14a	Proportions of responders in PGI-I at each follow-up visit for all patients on DFP – PP population
Table 14.2.1.15	Efficacy endpoints analysis for all patients on DFP: change in value at the end of study (Visit 4) – ITT population
Table 14.2.1.15a	Efficacy endpoints analysis for all patients on DFP: change in value at the end of study (Visit 4) – PP population
Table 14.2.1.15s	Efficacy endpoints analysis for all patients on DFP: change in value at the end of study (Visit 4) with imputed data – ITT population
Table 14.2.1.15.1	Efficacy endpoints analysis for all patients on DFP: change in value at the end of study (Visit 4) – ITT population and age at onset < 6 years
Table 14.2.1.15.2	Efficacy endpoints analysis for all patients on DFP: change in value at the end of study (Visit 4) – ITT population and age at onset ≥ 6 years
Table 14.2.1.15.3	Efficacy endpoints analysis for all patients on DFP: change in value at the end of study (Visit 4) – ITT population and DBS = Yes

Table 14.2.1.15.4	Efficacy endpoints analysis for all patients on DFP: change in value at the end of study (Visit 4) – ITT population and DBS = No
Table 14.2.1.15.5	Efficacy endpoints analysis for all patients on DFP: change in value at the end of study (Visit 4) – ITT population and Region = US
Table 14.2.1.15.6	Efficacy endpoints analysis for all patients on DFP: change in value at the end of study (Visit 4) – ITT population and Region = Europe
Table 14.2.1.15.7	Efficacy endpoints analysis for all patients on DFP: change in value at the end of study (Visit 4) – ITT population and Duration of disease > 5 years
Table 14.2.1.15.8	Efficacy endpoints analysis for all patients on DFP: change in value at the end of study (Visit 4) – ITT population and Duration of disease ≤ 5 years
Table 14.2.1.16	Efficacy endpoints analysis for all patients on DFP: proportions of responders in BAD total score and PGI-I at the end of study (Visit 4) – ITT population
Table 14.2.1.16a	Efficacy endpoints analysis for all patients on DFP: proportions of responders in BAD total score and PGI-I at the end of study (Visit 4) – PP population

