	Month 36	xx xx.xx (xx.x) xx.x (xx.x, xx.x)

Similar Table 14.2.1.2a will be based on PP population

§ DFP group includes all patients who ever took DFP during initial and extension study. This definition is applicable to all tables with this treatment group.

Table 14.2.1.3 Change in BAD score at each follow-up visit by treatment group in initial study – ITT population

	Visit	Placebo-DFP (N=xx)	DFP-DFP (N=xx)
Change in BAD n Mean (SD) Median (Min, Max) p -value [§]	Baseline	xx xx.xx (xx.x) xx.x (xx.x, xx.x)	xx xx.xx (xx.x) xx.x (xx.x, xx.x)
	Month 6	xx xx.xx (xx.x) xx.x (xx.x, xx.x) 0.xxxx	xx xx.xx (xx.x) xx.x (xx.x, xx.x) 0.xxxx
	Month 12	xx xx.xx (xx.x) xx.x (xx.x, xx.x) 0.xxxx	xx xx.xx (xx.x) xx.x (xx.x, xx.x) 0.xxxx
	Month 18	xx xx.xx (xx.x) xx.x (xx.x, xx.x) 0.xxxx	xx xx.xx (xx.x) xx.x (xx.x, xx.x) 0.xxxx
	Month 24	xx xx.xx (xx.x) xx.x (xx.x, xx.x) 0.xxxx	xx xx.xx (xx.x) xx.x (xx.x, xx.x) 0.xxxx
	Month 30	xx xx.xx (xx.x) xx.x (xx.x, xx.x) 0.xxxx	xx xx.xx (xx.x) xx.x (xx.x, xx.x) 0.xxxx

	Month 36	xx xx.xx (xx.x) xx.x (xx.x, xx.x) 0.xxxx	xx xx.xx (xx.x) xx.x (xx.x, xx.x) 0.xxxx
--	----------	--	--

§ p-value from paired t-test
 Similar Table 14.2.1.3a will be based on PP population

Table 14.2.1.4 Change in BAD score from baseline at each follow-up visit for all patients on DFP – ITT population

	Visit	DFP (N=xx)
Change in BAD n Mean (SD) Median (Min, Max) p-value [§]	Baseline	xx xx.xx (xx.x) xx.x (xx.x, xx.x)
	Month 6	xx xx.xx (xx.x) xx.x (xx.x, xx.x) 0.xxxx
	Month 12	xx xx.xx (xx.x) xx.x (xx.x, xx.x) 0.xxxx
	Month 18	xx xx.xx (xx.x) xx.x (xx.x, xx.x) 0.xxxx
	Month 24	xx xx.xx (xx.x) xx.x (xx.x, xx.x) 0.xxxx
	Month 30	xx xx.xx (xx.x) xx.x (xx.x, xx.x) 0.xxxx

	Month 36	xx xx.xx (xx.x) xx.x (xx.x, xx.x) 0.xxxx
--	----------	--

§ p-value from paired t-test

Similar Table 14.2.1.4a will be based on PP population

Table 14.2.1.5 BAD score per body region at each follow-up visit by treatment group in initial study – ITT population

Body Region	Visit	Placebo-DFP (N=xx)	DFP-DFP (N=xx)
Eyes n Mean (SD) Median (Min, Max)	Baseline	xx xx.xx (xx.x) xx.x (xx.x, xx.x)	xx xx.xx (xx.x) xx.x (xx.x, xx.x)
	Month 6	xx xx.xx (xx.x) xx.x (xx.x, xx.x)	xx xx.xx (xx.x) xx.x (xx.x, xx.x)
	Month 12	xx xx.xx (xx.x) xx.x (xx.x, xx.x)	xx xx.xx (xx.x) xx.x (xx.x, xx.x)
	Month 18	xx xx.xx (xx.x) xx.x (xx.x, xx.x)	xx xx.xx (xx.x) xx.x (xx.x, xx.x)
	Month 24	xx xx.xx (xx.x) xx.x (xx.x, xx.x)	xx xx.xx (xx.x) xx.x (xx.x, xx.x)

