	Visit	Placebo-DFP (N=xx)	DFP-DFP (N=xx)
Responder in PGI-I n (%)	Month 6	xx (xx.x)	xx (xx.x)
	Month 12	xx (xx.x)	xx (xx.x)
	Month 18	xx (xx.x)	xx (xx.x)
	Month 24	xx (xx.x)	xx (xx.x)
	Month 30	xx (xx.x)	xx (xx.x)
	Month 36	xx (xx.x)	xx (xx.x)

Similar Table 14.2.1.13a will be based on PP population

Table 14.2.1.14 Proportions of responders in PGI-I at each follow-up visit for all patients on DFP – ITT population

	Visit	DFP (N=xx)
Responder in PGI-I n (%)	Month 6	xx (xx.x)
	Month 12	xx (xx.x)
	Month 18	xx (xx.x)
	Month 24	xx (xx.x)
	Month 30	xx (xx.x)
	Month 36	xx (xx.x)

Similar Table 14.2.1.14a will be based on PP population

Table 14.2.1.15 Efficacy endpoints analysis for all patients on DFP: change in value at the end of study (Visit 4) – ITT population

	Visit	Score n Mean (SD)	Change from Baseline n Mean (SD)	p-value [§]
BAD Total Score	Baseline	xx xx.xx (xx.x)		
	Visit 4	xx xx.xx (xx.x)	xx xx.xx (xx.x)	0.xxxx
PGI-I	Visit 4		xx xx.xx (xx.x)	0.xxxx
Eyes score	Baseline	xx xx.xx (xx.x)		
	Visit 4	xx xx.xx (xx.x)	xx xx.xx (xx.x)	0.xxxx
Repeat for other body regions

§ p-value from paired t-test

Similar Table 14.2.1.15a will be based on PP population

Similar Table 14.2.1.15s will be based on missing data imputed as sensitivity analysis

Similar Tables 14.2.1.15.1 and 14.2.1.15.2 will be based on ITT population and Age at onset of motor symptoms (Age <6 vs. Age ≥6)

Similar Tables 14.2.1.15.3 and 14.2.1.15.4 will be based on ITT population and DBS (Deep Brain Stimulation Yes vs. No)

Similar Tables 14.2.1.15.5 and 14.2.1.15.6 will be based on ITT population and Region (US vs. Europe)

Similar Tables 14.2.1.15.7 and 14.2.1.15.8 will be based on ITT population and Duration of disease at baseline (>5 years vs. ≤5 years)

Table 14.2.1.16 Efficacy endpoints analysis for all patients on DFP: proportions of responders in BAD total score and PGI-I at the end of study (Visit 4) – ITT population

	Visit	(N=xx)
Responder in BAD total score n (%) (95% CI)	Visit 4	xx (xx.x) (xx.x, xx.x)
Responder in PGI-I n (%) (95% CI)	Visit 4	xx (xx.x) (xx.x, xx.x)

Similar Table 14.2.1.16a will be based on PP population

Similar Table 14.2.1.16s will be based on missing data imputed as sensitivity analysis

Table 14.2.1.17 Trend analysis by MMRM model on BAD total score and by body region for all patients – ITT population

Dependent Variable	Time slope	95% CI of the Slope	p -value
BAD Total Score	xx.x	(xx.xx xx.x)	0.xxxx
Eyes	xx.x	(xx.xx xx.x)	0.xxxx

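### The secondary all-patients Visit 4 analysis of BAD pools 36-month change for continuers with 18-month change for switchers, and the subgroup tables, imputed tables and responder confidence intervals exist only in that pooled form

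*SAP*

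**What the plan says.** SAP Section 4 takes baseline as the point before deferiprone starts. For patients on deferiprone in the initial study, "Visit 4 (Week 78) will be Year 3 (month 36"); for those on placebo, "Visit 4 (Week 78) will be Year 1.5 (month 18"). Protocol 9.1.2 defines the time points in the same way.

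SAP 4.3.1, under all patients, tests the change to the end of study, meaning "Visit 4, month 18 or 36 as defined in section 4". The table is titled "Efficacy endpoints analysis for all patients on DFP: change in value at the end of study (Visit 4"). Its shell in SAP Section 7 has a baseline row and a single Visit 4 row for each BAD score, with no split by initial-study group or month. A footnote to the Table 14.2.1.2 shell says that the "DFP group includes all patients who ever took DFP during initial and extension study". Table 14.2.1.16 gives responder proportions with 95% confidence intervals in the same pooled form.

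The subgroup tables reuse the shell, for example "Similar Tables 14.2.1.15.5 and 14.2.1.15.6 will be based on ITT population and Region (US vs. Europe"). There are eight, 14.2.1.15.1 to 14.2.1.15.8: two levels each of age at onset, deep brain stimulation, region and disease duration. SAP 3.2 gives the enrolled numbers: "44 originally randomized to the deferiprone group and 24 in the placebo group".

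**The concern.** The protocol describes PKAN as progressive, so the expected BAD change depends on elapsed time. A mean that combines two durations is set partly by how many continuers and switchers happened to enrol. It estimates the change at neither month 18 nor month 36. The same holds for the responder proportion, because a total-score change of zero or less may be harder to sustain over three years than over eighteen months.

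The subgroup tables are the most exposed. SAP 4.3.2 says they are meant to explore differences across subgroups, so readers will compare them. If one subgroup contains more continuers, its mean refers to a longer time on drug. Part of any difference between subgroups may then be duration alone, and no planned table would let a reader tell.

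**Working it through.** The documents give no power calculation, BAD change or standard deviation, so there is no design figure to reproduce. The one check available is enrolment: 44 + 24 = 68, which agrees with SAP 3.2.

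**What the pooled row estimates**

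- Share of continuers: 44/68 = 64.7%.
- Mean planned time on drug: (44 × 36 + 24 × 18)/68 = 2016/68 = 29.6 months.
- Pooled mean: (44 × m36 + 24 × m18)/68, where m18 and m36 are the mean changes at those months.
- Under linear change (m36 = 2 × m18): (88 + 24)/68 = 1.65 times m18, and 1.65/2 = 0.82 times m36.

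| Assumed m18 | Assumed m36 | Pooled mean |
|---|---|---|
| 1 | 2 | 1.65 |
| 2 | 4 | 3.29 |
| 3 | 6 | 4.94 |
| 0 | 2 | 1.29 |
| 2 | 2 | 2.00 |

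The point values are illustrative. In the last row nothing changes after month 18, and pooling does no harm. Early terminators widen the spread of durations further, because under SAP 3.5 "the last observation will be used to calculate the change from baseline for patients terminated early".

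**Subgroups**

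Suppose two subgroups A and B progress identically and have continuer shares pA and pB. The apparent difference is (pA − pB) × (m36 − m18).

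| Share gap | m36 − m18 = 1 | = 2 | = 3 |
|---|---|---|---|
| 0.20 | 0.2 | 0.4 | 0.6 |
| 0.30 | 0.3 | 0.6 | 0.9 |
| 0 | 0 | 0 | 0 |

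For a gap of 0.30, take shares of 80% and 50%. Mean durations are 0.8 × 36 + 0.2 × 18 = 32.4 and 0.5 × 36 + 0.5 × 18 = 27.0 months. Under linearity that is a 20% difference in expected change (32.4/27.0 = 1.20).

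The chance of such gaps follows from the exact hypergeometric distribution (68 patients, 44 continuers). The subgroup sizes are assumed, because the documents do not give them.

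| Subgroup split | P(gap ≥ 0.20) | P(gap ≥ 0.30) |
|---|---|---|
| 34/34 | 7.5% | 0.5% |
| 20/48 | 16.3% | 1.1% |
| 14/54 | 11.4% | 2.5% |

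**What is already reported by duration**

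- Table 14.2.1.4: BAD total change by month for all patients on drug, with paired tests. Its month-36 row can contain only continuers. Table 14.2.1.3 gives the same by initial-study group.
- Table 14.2.1.8: body regions by month.
- Table 14.2.1.10: BAD responders by month, as n (%) without confidence intervals.
- Table 14.2.1.17: a slope on continuous time.
- Table 14.2.3.1: both groups at a common month 18, BAD total only.

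None of these is repeated by subgroup or with the imputed data, and none gives a responder confidence interval.

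**The case against.** The strongest reply is that the SAP follows a disclosed, protocol-defined endpoint and already supplies most of the remedy. This largely stands. A paired t-test of each patient's own change is a legitimate test of whether the mean change to end of study is zero; what pooling blurs is its interpretation. For BAD in the whole population, the tables listed above give duration-specific results.

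The priority of the endpoint also matters. A reader might take the pooled row as the trial's headline result. The documents do not support that: the primary objective is safety and BAD change is secondary. The subgroup analyses sit under an exploratory heading, and their shells contain no between-subgroup test.

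Two further inferences go too far. One is that a subgroup with more switchers will look better. That needs unequal shares as well as worsening between months 18 and 36, and the documents quantify neither. The other is that the 18/36-month factors apply to PGI-I. Protocol 7.1.2 has it rated from extension Visit 1 in both groups, although Appendix 5 is less specific. Its mixture is of the first and second 18 months on drug.

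Finally, one might make month 18 the all-patients endpoint. For the 44 continuers that value comes from extension Visit 1, so their extension follow-up would drop out of a long-term study, and the endpoint would depart from the protocol. Continuers also had to complete their first 18 months to enrol, while switchers' first 18 months on drug can include early terminators. That is a debatable trade-off, not a needed correction.

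None of this covers the subgroup tables, the imputed versions or the responder confidence intervals.

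**Conclusion.** The point holds for BAD, in a limited form. The pooled Visit 4 mean and responder proportion in Tables 14.2.1.15 and 14.2.1.16 and their variants correspond to no defined time on drug. Under linear change the mean lies at 1.65 times the 18-month and 0.82 times the 36-month value. Overall, a reader can recover duration-specific results from other tables. By subgroup, with imputed data, or with a confidence interval for responders, a reader cannot.

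A spurious subgroup difference is possible, not expected. A share gap of 0.20 or more has a 7.5% to 16.3% chance for the splits examined, and a gap of 0.30 or more 0.5% to 2.5%. These figures assume that continuers and switchers are spread at random over the subgroups. Selection on the way from 89 randomised through 76 completers to 68 enrolled could add imbalance. If shares are equal, or BAD does not change between months 18 and 36, the artefact is zero. This is an inexpensive improvement to a secondary analysis and does not show that the planned test is invalid.

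**What to change.** In Tables 14.2.1.15, 14.2.1.15a, 14.2.1.15s, 14.2.1.15.1 to 14.2.1.15.8, 14.2.1.16, 14.2.1.16a and 14.2.1.16s:

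- Keep the protocol-defined pooled Visit 4 row, labelled as a mixture of 18 and 36 months on deferiprone.
- Add rows by initial-study group: Placebo-DFP at month 18 and DFP-DFP at month 36, with DFP-DFP at month 18 as an option. Give 95% confidence intervals for responders in each row.
- Note in each row that early terminators contribute their last observation. In the imputed versions, state which month supplies the worst score.
- Base any subgroup statement on the group-specific rows.
- Split PGI-I by group too, label it as rated from extension Visit 1, and do not present it as a 36-month change.

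The data and the month-18 and month-36 windows already exist. The costs are smaller numbers per row (at most 44 and 24, and fewer within subgroups), longer tables, and a note in the study report, because Protocol 9.4 requires changes to the planned methods to be documented there.
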